## **INTRODUCTION**

Lupus nephritis (LN) may affect approximately half of patients with Systemic Lupus Erythematosus (SLE). LN is a major cause of morbidity and the most important predictor of mortality in patients with SLE (1,2). Some 5-20% of patients with LN may develop end-stage renal disease within 10 years of follow-up from the time of diagnosis (3). Other studies have described progression to end-stage renal disease in 10-30% of patients with LN (4,5).

The European League Against Rheumatism (EULAR), the European Renal Association (ERA) and the European Dialysis and Transplant Association (EDTA) have recently updated their recommendations for the management of LN. These recommend the use of intravenous (IV) methylprednisolone boluses followed by lower doses of oral glucocorticoids (GC) and place mycophenolate mofetil (MMF) and the European regimen of cyclophosphamide (CYC) as the immunosuppressive drugs of first choice, with the IV CYC regimen for certain more aggressive cases. They also consider the use of "multitarget therapy" based on the combination of tacrolimus (TAC) and MMF and GC in patients with proteinuria in the nephrotic range who have not responded to the first line of treatment. For refractory active renal disease, they recommend as an alternative the use of rituximab (RTX) 1000 mg IV repeated after 15 days (6).

Recently, belimumab has been shown to be significantly more effective than placebo in the treatment of patients with active LN (7). This finding will lead to positioning belimumab in the therapeutic algorithm for LN.

However, in clinical practice these immunosuppressive drugs are not always effective in the treatment of LN, and even one in 3 patients with an initial favorable response may experience renal recurrence (3).

The choice of the appropriate treatment for LN and its early initiation are key to improve the prognosis of these patients and to avoid progression to chronic renal failure.

The identification of biomarkers capable of predicting the response (or lack thereof) to one or another therapy at the time of LN diagnosis would allow to implement precision medicine, thus constituting a revolution in the treatment of patients with LN. Being able to make personalized therapeutic decisions, based on the biological characteristics of each patient's renal sample, allows more targeted treatments with greater specificity to be established.

The **objective** of this project is to analyze histopathological biomarkers in the renal biopsy to predict the renal response to the different drugs used in the treatment of LN. This would contribute to a more specific and cost-effective therapeutic strategy.

## **PATIENTS AND METHODS**

### **Inclusion criteria:**

Patients with a diagnosis of SLE according to the 1997 American College of Rheumatology (ACR) criteria (8).

Diagnosis of lupus nephritis type 3,4,5 or mixed forms of the above according to the International Society of Nephrology (ISN)/Renal Pathology Society (RPS) classification of LN (9).

Date of performance of the renal biopsy: year 2000 or later. The reason for this time frame is the theoretical homogenization in the therapeutic management of LN with the introduction of MMF into the therapeutic armamentarium of LN and the extension of the use of the European intravenous cyclophosphamide guideline.

Availability of the patient's first renal biopsy specimen preserved for re-evaluation.

Availability of essential clinical data to carry out the study.

Signature of the informed consent by the patient.

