#### Exclusion criteria:

Refusal by the patient to sign the informed consent.

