#### Sample size

For this proof-of-concept study, our objective is to analyze around **60 renal biopsy** samples (expandable according to the results obtained).

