#### Methods:

The following **general variables** will be collected:

- demographic data: age, sex, ethnicity.
- clinical data on SLE:
  - diagnosis and chronological data: time of SLE diagnosis, time of LN diagnosis, time from SLE diagnosis to LN.
  - 1997 ACR SLE classification criteria,
  - activity: involvement of different organs and systems by SELENA-SLEDAI (10) at the time of LN diagnosis and at the time of the last evaluation of the patient (or death, if applicable).
  - damage: by item and by domain according to the Systemic Lupus International Collaborating Clinics Damage Index (SDI) (11) at the time of LN diagnosis and at the time of the last evaluation of the patient (or death, if applicable).
  - comorbidity: arterial hypertension, diabetes, dyslipemia, smoking habit, severe infections, neoplasms, etc. at the time of LN diagnosis and at the time of the last evaluation of the patient (or death, if applicable).
- laboratory data at the time of LN diagnosis and at the time of the last evaluation of the patient (or death, if applicable):
  - blood (general tests): acute phase reactants (erythrocyte sedimentation rate and C-reactive protein), full blood count, creatinin, glomerular filtration rate, blood urea nitrogen, liver function tests, lipid profile.

- blood (serological tests): complement (C3 and C4), levels of anti-dsDNA antibodies, antiphospholipid antibodies: anticardiolipin (Ig M and Ig G), anti-beta2GP-1 (Ig M and Ig G), lupus anticoagulant.
- urine: hematuria, piuria, proteinuria, casts.
- histopathological markers of renal biopsy:
  - histological class according to the 2003 ISN/RPS classification (9).
  - National Institutes of Health (NIH) activity index (12): score (maximum 24) and by item (endocapillary hypercellularity, neutrophils/karyorrhexis, hyaline deposits/wire loops, fibrinoid necrosis, cellular or fibrocellular crescents, interstitial inflammation).
  - National Institutes of Health (NIH) chronicity index (12): score (maximum 12) and by item (global glomerulosclerosis, fibrous crescents, tubular atrophy, interstitial fibrosis).
  - markers related to B lymphocytes which may include but is not limited to: CD19, CD20 and CD138.
  - markers related to BLYS (B lymphocyte stimulator) and its functional consequences which may include but is not limited to expression of BLYS and its receptors: BAFF-R, BCMA and TACI.

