  - markers related to other cell lineages which may include but is not limited to: CD3 for T cells and CD68 for macrophages.
  - markers whose determination in urine has proved useful in the diagnosis and follow-up of LN which may include but is not limited to the proinflammatory cytokine Monocyte Chemoattractant Protein-1 (MCP-1) and the Neutrophil Gelatinase Associated Lipocalin (NGAL).
- SLE therapeutical data (including duration of the treatment):
  - treatments for SLE prior to the diagnosis of LN: antimalarials, glucocorticoids (maximum dose), immunosuppressants: azathioprine (AZA), mophetil mycophenolate (MMF), cyclophosphamide (CYC); biological therapies: belimumab, rituximab.
  - treatment of LN: glucocorticoids (maximum dose), immunosuppressants: AZA, MMF, CYC; biological therapies: belimumab, rituximab.
  - therapeutical data of comorbidities (including duration of the treatment): antihypertensive agents, oral antidiabetics, insulin, hypolipidemic drugs.
- Evolution/prognosis of SLE: accumulated damage by using SDI (11) (by item and by domain), comorbidities accrual, severe infections, organ failure, death.

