**Variables will be collected to establish different patterns of response to treatment and evolution of LN:**

- a) complete renal response, defined according to EULAR/ERA-EDTA recommendations (13): proteinuria  $<0.5$  g/24 hours and (near) normal estimated GFR.
- b) partial renal response, defined according to EULAR/ERA-EDTA recommendations (13):  $\geq 50\%$  proteinuria reduction to subnephrotic levels and (near) normal eGFR
- c) no response: all the other cases.
- d) proteinuria levels at 12 months of treatment,
- e) renal relapse as defined as reproducible increase in uPCR to  $>1$  g if the baseline value was  $<0.2$  g, to  $>2$  g if the baseline value was between  $0.2$  g and  $1$  g, or more than twice the value at baseline if the baseline value was  $>1$  g AND/OR reproducible decrease in GFR of  $>20\%$ , accompanied by proteinuria ( $>1$  g), and/or RBC and/or WBC cellular casts (yes/no and number of flares), e) time to first flare, f) chronic renal failure,
- f) end-stage renal disease requiring dialysis and/or renal transplantation.

Data collection will be based on the clinical history of the patients included in the study.

Confidentiality will be respected in accordance with RD 1720/2007 and the Data Protection Laws. Approval will be requested from the **Galician Clinical Research Ethics Committee (CEIC)** as well as from the CEIC of each center, if necessary.

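### Entry needs the patient's own signature, up to about 20 years after biopsy, so as written the cohort holds only survivors to consent although the plan also means to record death

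*Combined protocol and SAP*

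**What the plan says.** Under Inclusion criteria, the combined protocol and SAP lists "Signature of the informed consent by the patient" and "Date of performance of the renal biopsy: year 2000 or later"; the specimen is the patient's first biopsy. The single exclusion criterion is "Refusal by the patient to sign the informed consent". Sample size sets a target of around 60 biopsies, "expandable according to the results obtained". Timelines places ethics submission and approval in months 1–3, signatures in months 4–6 and chart review in months 7–12.

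Death appears in two parts of Methods. Activity, damage, comorbidity and laboratory data are to be taken at LN diagnosis and "at the time of the last evaluation of the patient (or death, if applicable", and the prognosis item lists "comorbidities accrual, severe infections, organ failure, death".

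The separate list of response and evolution variables includes "end-stage renal disease requiring dialysis and/or renal transplantation" but not death. Below that list the plan states: "Data collection will be based on the clinical history of the patients included in the study". Statistical Analysis takes the renal outcomes as dependent variables and names no analysis of death.

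On approvals, the visible text mentions only the regional ethics committee and, where necessary, the committee of each centre. It does not mention a waiver, next-of-kin consent or deceased patients.

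**The concern.** The study is retrospective: an old block is restained and an old chart is read. Neither step needs the patient to be alive, but the entry rule does. An eligible patient who died between biopsy and months 4–6 cannot sign, so as written that patient stays out even if block and chart are complete.

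Two things follow. First, the entry rule and the death fields do not fit together, because almost all deaths since biopsy fall before the point at which a patient can enter. Second, the cohort describes patients who were alive and consented, and the plan does not say so. The Introduction calls LN the leading predictor of mortality in SLE, so survival to consent may not be neutral with respect to disease course. If patients with poor renal courses die more often, those courses are thinned out. No visible section plans a log of eligible biopsies, so a reader could not judge how selected the roughly 60 are. The general sentence on missing data in Statistical Analysis does not reach patients who never enter.

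**Working it through.** **The plan's own figure.** The target of around 60 has no formula or inputs. It can be neither reproduced nor refuted, and it is not disputed here.

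**Step 1: longest gap from biopsy to signature.** The calendar start is not stated. The Bibliography cites a randomised belimumab trial in LN dated 17 September 2020, so the plan is not older than that. From 1 January 2000 to that date is 20.7 years; from 31 December 2000 it is 19.7 years. Both are lower bounds for a biopsy done on those dates, since signatures start only in month 4. Recent biopsies also qualify, so this is the extreme and not the typical gap.

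**Step 2: window in which a death can be recorded.** On a time axis in months, signatures run from 3 to 6 and chart review from 6 to 12.
- Shortest gap: 6 − 6 = 0. Longest: 12 − 3 = 9.
- Mean if both dates are uniform: 9.0 − 4.5 = 4.5.
- For gaps g up to 3 months, P(gap ≤ g) = g²/36. Setting this to 0.05 gives 1.34; by symmetry the 95th percentile is 9 − 1.34 = 7.66.

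**Step 3: deaths that could be recorded among 60.** The documents give no death rate. I assume h = 1% to 3% per year.
- Expected number = 60 × [1 − (1 − h)^(4.5/12)] = 0.23, 0.45 and 0.68 for h = 1%, 2% and 3%.
- With the 9-month maximum for every patient: 0.45, 0.90 and 1.36.
- Chance of recording none at 4.5 months: 0.80, 0.63 and 0.50.

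**Step 4: deaths before consent, same assumed rates.** Lost before consent after t years = 1 − (1 − h)^t. Share of all deaths up to chart review that fall before consent = lost / [lost + (1 − lost) × P(death in window)].

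| Biopsy age (years) | Lost before consent | Share before consent, 4.5-month window | Same, 9-month window |
|---|---|---|---|
| 1 | 1–3% | 73% | 57–58% |
| 5 | 5–14% | 93–94% | 87–88% |
| 10 | 10–26% | 97% | 93–94% |
| 20 | 18–46% | 98–99% | 97% |

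The loss column depends directly on the assumed rate. The share columns hardly do: they are close to t/(t + window), for example 10/(10 + 0.375) = 96%. They restate the timeline and are not evidence of harm.

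**Step 5: what selection could do to the results (illustration).** Suppose true complete response is 50%.
- If 5% of responders and 20% of non-responders die before consent, the share seen among survivors is 0.475/(0.475 + 0.400) = 54%.
- At 2% and 5% it is 51%; at 10% and 30% it is 56%.

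For a marker, survivor odds ratio = true odds ratio × (S11 × S00)/(S10 × S01), where S is survival to consent by marker and outcome. The factor is 1 when survival depends only on the outcome. It is also 1 when survival is a marker effect times an outcome effect, because the terms cancel.

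Take non-response of 65% against 35%, a true odds ratio of 3.45, with 5% death in responders:
- 10% death in non-responders whatever the marker: 3.45, unchanged.
- 20% in marker-positive and 10% in marker-negative non-responders: 3.45 × 0.80/0.90 = 3.07.
- 35% and 15%: 3.45 × 0.65/0.85 = 2.64.

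**The case against.** The strongest reply is that the omission cannot be confirmed. Consent pages are removed from this copy, and a waiver or deceased-patient route would normally sit there or in the ethics material. The visible text is also mixed: Methods asks for data at death and the only exclusion is refusal, so the authors may have meant to include deceased patients. This stands as a limit. A reader might infer that the plan has no route at all; the documents show only that none is visible. The signature criterion would still need rewording to agree with any such route and with Methods.

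A second reply is that death is not what the study analyses. The objective is to predict renal response, and counts of recordable deaths show no damage to that. This also stands. Inferring that a mortality endpoint has failed would be wrong, because death is neither on the response and evolution list nor in the planned analyses.

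Third, a reader might infer that the marker odds ratios are biased or that ESRD drops out of the data. Neither is supported. Living patients on dialysis or with a transplant can sign, so ESRD may be under-represented but is not excluded. Odds-ratio bias needs survival that depends on marker and outcome together in a non-multiplicative way, and nothing in the documents shows that. The values 3.07 and 2.64 rest on invented death rates.

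Finally, the 18–46% loss belongs to 20-year-old biopsies under an assumed constant rate; at one year it is 1–3%. The mix of biopsy ages is not given.

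**Conclusion.** The point holds in a limited form. It rests on a stated entry rule and the stated timeline: as written, the cohort is conditioned on survival to consent, and this conflicts with the plan to record death. The firm figures are the longest gap of about 20 years and the recording window of 0 to 9 months; the mean of 4.5 months assumes uniform dates. Everything that uses a death rate is illustration on an assumed 1–3% per year.

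If mortality is higher after poor renal courses, severe outcomes such as ESRD are under-represented, by an amount the documents do not allow one to state. Conclusions then apply to consenting survivors, and the plan should say so. No bias in marker odds ratios is shown. For a proof-of-concept study this is a matter of who enters and what the results describe. It is worth correcting because correction is cheap; it does not invalidate the design.

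**What to change.** 1. In the ethics submission planned for months 1–3, and at centre committees where needed, request approval to use the archived block and chart of eligible patients who have died.
2. Reword the criterion so that it agrees with Methods: *signed consent by living patients; for deceased patients, use as approved by the ethics committee*.
3. Log every eligible biopsy by vital status and consent outcome (signed, refused, not traced, died) and report that flow. Living patients who cannot be traced stay out and are counted in the log.
4. Repeat the main analysis in living consenters only, as a sensitivity check.
5. If approval is refused, report any post-consent deaths descriptively and state that conclusions apply to patients alive and consenting at months 4–6.

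The cost is one added request, one reworded criterion, a screening log and one repeated analysis; the laboratory and chart methods do not change. The committee may refuse or set conditions, and more than one committee may be involved. Deceased patients may also become somewhat over-represented, because living patients must be traced and agree. For example, if 10% of eligible patients have died and all enter, while 70% of the living consent (both assumed), the deceased share is 10/(10 + 0.70 × 90) = 10/73 = 13.7%. That is closer to 10% than the present 0%, and the log makes it visible.

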#### Exclusion criteria:

Refusal by the patient to sign the informed consent.

#### Sample size

For this proof-of-concept study, our objective is to analyze around **60 renal biopsy** samples (expandable according to the results obtained).

#### Methods:

The following **general variables** will be collected:

- demographic data: age, sex, ethnicity.
- clinical data on SLE:
  - diagnosis and chronological data: time of SLE diagnosis, time of LN diagnosis, time from SLE diagnosis to LN.
  - 1997 ACR SLE classification criteria,
  - activity: involvement of different organs and systems by SELENA-SLEDAI (10) at the time of LN diagnosis and at the time of the last evaluation of the patient (or death, if applicable).
  - damage: by item and by domain according to the Systemic Lupus International Collaborating Clinics Damage Index (SDI) (11) at the time of LN diagnosis and at the time of the last evaluation of the patient (or death, if applicable).
  - comorbidity: arterial hypertension, diabetes, dyslipemia, smoking habit, severe infections, neoplasms, etc. at the time of LN diagnosis and at the time of the last evaluation of the patient (or death, if applicable).
- laboratory data at the time of LN diagnosis and at the time of the last evaluation of the patient (or death, if applicable):
  - blood (general tests): acute phase reactants (erythrocyte sedimentation rate and C-reactive protein), full blood count, creatinin, glomerular filtration rate, blood urea nitrogen, liver function tests, lipid profile.

- blood (serological tests): complement (C3 and C4), levels of anti-dsDNA antibodies, antiphospholipid antibodies: anticardiolipin (Ig M and Ig G), anti-beta2GP-1 (Ig M and Ig G), lupus anticoagulant.
- urine: hematuria, piuria, proteinuria, casts.
- histopathological markers of renal biopsy:
  - histological class according to the 2003 ISN/RPS classification (9).
  - National Institutes of Health (NIH) activity index (12): score (maximum 24) and by item (endocapillary hypercellularity, neutrophils/karyorrhexis, hyaline deposits/wire loops, fibrinoid necrosis, cellular or fibrocellular crescents, interstitial inflammation).
  - National Institutes of Health (NIH) chronicity index (12): score (maximum 12) and by item (global glomerulosclerosis, fibrous crescents, tubular atrophy, interstitial fibrosis).
  - markers related to B lymphocytes which may include but is not limited to: CD19, CD20 and CD138.
  - markers related to BLYS (B lymphocyte stimulator) and its functional consequences which may include but is not limited to expression of BLYS and its receptors: BAFF-R, BCMA and TACI.
  - markers related to other cell lineages which may include but is not limited to: CD3 for T cells and CD68 for macrophages.
  - markers whose determination in urine has proved useful in the diagnosis and follow-up of LN which may include but is not limited to the proinflammatory cytokine Monocyte Chemoattractant Protein-1 (MCP-1) and the Neutrophil Gelatinase Associated Lipocalin (NGAL).
- SLE therapeutical data (including duration of the treatment):
  - treatments for SLE prior to the diagnosis of LN: antimalarials, glucocorticoids (maximum dose), immunosuppressants: azathioprine (AZA), mophetil mycophenolate (MMF), cyclophosphamide (CYC); biological therapies: belimumab, rituximab.
  - treatment of LN: glucocorticoids (maximum dose), immunosuppressants: AZA, MMF, CYC; biological therapies: belimumab, rituximab.
  - therapeutical data of comorbidities (including duration of the treatment): antihypertensive agents, oral antidiabetics, insulin, hypolipidemic drugs.
- Evolution/prognosis of SLE: accumulated damage by using SDI (11) (by item and by domain), comorbidities accrual, severe infections, organ failure, death.

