## **STATISTICAL ANALYSIS**

In the descriptive study, numerical variables will be expressed as mean  $\pm$  standard deviation (SD) or median and interquartile range (IQR), depending on whether the distribution is normal or not, respectively. We will establish 2 groups of patients, according to the response to treatment and the clinical evolution of the patient with LN (i.e., complete remission yes/no). To establish differences between patients in these 2 groups, we will use the  $\chi^2$  test for categorical variables or Fisher's exact test when the expected frequencies are small, the t-Student test for normal continuous variables, and the Mann-Whitney U test for variables with non-normal distribution.

Different methods to analyze and/or mitigate the missing data problem will be used.

The percentage of positive cells and staining intensity will be correlated with the different patterns of response to treatment and evolution of LN.

Univariate and multivariate linear logistic regression analyses will be performed to explore the relationships between the different variables studied (clinical, histopathological, therapeutic...) and the presence of the different renal outcomes (dependent variable). Values of  $p < 0.05$  will be considered significant.

We will carry out other different statistical methods according to the results that we observe from our initial analysis.

Statistical analyses will be performed by the Statistical Specialist of the IRIDIS Group.

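### LN treatment is recorded without a time window, so duration, later-line drugs and, less certainly, maximum glucocorticoid dose can be partly consequences of the renal outcome they may be used to explain

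*Combined protocol and SAP*

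**What the plan says.** Under Methods, in the block headed "SLE therapeutical data (including duration of the treatment"), the protocol lists "treatment of LN: glucocorticoids (maximum dose), immunosuppressants: AZA, MMF, CYC; biological therapies: belimumab, rituximab". It gives no window, line of therapy or route for the glucocorticoid maximum, and no start or stop anchor for duration.

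Other variables are anchored. Activity, damage, comorbidity and laboratory data are taken "at the time of LN diagnosis and at the time of the last evaluation of the patient". The preceding treatment item, "treatments for SLE prior to the diagnosis of LN", is bounded by the LN diagnosis and is not affected by this point.

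The Statistical Analysis section plans univariate and multivariate regressions to "explore the relationships between the different variables studied (clinical, histopathological, therapeutic...) and the presence of the different renal outcomes (dependent variable"). It mentions no landmark, time-varying exposure or other handling of treatment that changed after the outcome.

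In the list of response patterns, complete and partial response carry no assessment time, and the third category is "no response: all the other cases". Only "proteinuria levels at 12 months of treatment" has a fixed time.

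The Introduction describes a tacrolimus, MMF and glucocorticoid combination "in patients with proteinuria in the nephrotic range who have not responded to the first line of treatment", and rituximab for refractory disease. Rituximab is on the Methods list of LN treatments.

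**The concern.** An explanatory variable for response should be fixed before response is known. An open-window maximum can only rise with later courses. The duration of a drug depends partly on whether it was stopped for failure or kept because it worked. A drug given only after failure marks the failure itself.

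The data come from clinical histories of patients biopsied in 2000 or later, so a chart may hold years of later treatment. A regression on such variables can show an association with response when the initial treatment has no effect. A larger sample, which the protocol allows, would make a false association more significant, not less.

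The stated objective is to predict response to the different drugs, and for that the analyst must know which treatment came before the response.

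**Working it through.** **The plan's own figure.** The only relevant number is the target of around 60 biopsies. It comes with no effect size, response rate or power, so it cannot be reproduced. It serves here only as the n of the simulations.

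**Inputs from the documents.** n = 60; significance at p < 0.05; up to one in 3 initial responders may have a renal recurrence (Introduction); initial IV boluses followed by lower oral doses (Introduction).

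**Assumptions (not in the documents).** Half of patients respond. Initial dose is log-normal with log-scale SD 0.5 and unrelated to response. A share q of non-responders later has the dose doubled, or the drug stopped early. Groups are compared by a two-sided Mann-Whitney test. There is no true effect, so every significant result is false.

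**Expected shift in maximum dose.** Doubling adds ln 2 = 0.693 on the log scale, or 0.693 / 0.5 = 1.39 SD per escalated patient.

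- Only non-responders escalated: shift = q × 1.39 SD. For q = 0.2, 0.4, 0.6 this is 0.28, 0.55, 0.83 SD, higher in non-responders.
- One third of responders also re-treated at double dose: shift = (q − 1/3) × 1.39 SD. This is −0.18, 0.09, 0.37 SD. At q = 0.2 the sign is reversed.

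**Simulated share of studies with p < 0.05.**

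| Scenario | q = 20% | q = 40% | q = 60% |
|---|---|---|---|
| Maximum dose, only non-responders escalated | 14% | 43% | 78% |
| Same, boluses set the maximum in half of patients | 6% | 8% | 11% |
| Same, boluses set the maximum in 80% or all | about 5% | about 5% | about 5% |
| Maximum dose, one third of responders also doubled | 10% | 4-6% | 21% |
| Duration: failures stop at 3-12 months, all others at 12-48 | 28% | 77% | 99% |
| Duration: exponential, mean 36 months, cut at 12 months in failures | 10-11% | 30-31% | 51-52% |

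Initial dose alone is significant in 5-6% of studies in the first scenario. With 2,000 runs the standard error near 43% is √(0.43 × 0.57 / 2000) = 1.1 percentage points. Repeat runs gave 14-17%, 42-44% and 78-80% for the first row, so these are rounded illustrations.

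**A second model** (normal dose, t-test, response rate 30%, 50% or 70%, later excess of 0.5 to 2 SD) gave these rates for maximum dose: 4-6% with no non-responder escalated, 5-11% at a 10% share, 7-36% at 25%, and 14-86% at 50%. Dose restricted to the period before assessment stayed at 4-6% throughout. Duration (exponential, cut at 12 months) gave 13-14% at a 25% share and 35-40% at 50%.

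**Drugs given after failure** need no simulation. If rituximab is given because the first line failed, its presence in the record identifies a non-responder.

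**The case against.** The strongest objection concerns dose. The Introduction describes IV boluses followed by lower oral doses, so the maximum may often be reached before response is known. Nowhere does it say that the glucocorticoid dose is raised after failure. This stands: a reader might infer that outcome drives the recorded dose, but the documents support only that it can. The protocol does not say whether boluses count towards the maximum. If they do not, this protection is weaker.

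Second, a reader might infer that the regression will show higher dose predicting non-response. The documents' own relapse figure argues against a fixed direction, because re-treated responders also gain a higher maximum. Direction is open for duration too: the protocol does not say whether it is per drug or for LN treatment as a whole, and total duration could be longer in non-responders.

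Third, the steepest duration figures use ranges for failures and others that do not overlap. They are near a worst case.

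Fourth, the study is a proof of concept about biopsy markers, taken from the first biopsy, which later treatment cannot change. Therapeutic variables are named only as a class, for exploration. This limits the reach of the point: no simulation here includes a marker, and nothing shows that the marker results are invalid. It does not remove the defect, since the plan permits these variables in multivariate models and a proof-of-concept label does not protect against systematic bias.

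**Conclusion.** The point holds in a limited form. The plan as written lets treatment that followed the outcome enter as an explanatory variable. The case is firmest for drugs given after failure and for duration, and less certain for maximum glucocorticoid dose.

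Under the dose-doubling model with 60 patients, half of them responding, and 20-60% of non-responders affected, the false-positive rate runs from about 5% to about 80% for maximum dose. Under the two duration models it runs from about 10% to 99%. All shares, and the size of the dose increase, are assumptions. If no treatment changes after non-response or relapse, there is no bias. The documents establish neither a particular size nor a particular direction. This is a cheap improvement, not a flaw that undermines the marker objective.

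**What to change.** 1. In the list of response patterns, state one assessment time for complete, partial and no response, for example the 12-month point already used for proteinuria. Without it the window below cannot be defined.
2. In Methods, record initial LN treatment (drug and glucocorticoid dose) in a fixed window from treatment start that closes before that assessment and before any change for inadequate response. Say whether boluses count towards the maximum. Record later treatment separately.
3. In Statistical Analysis, use only the windowed variables as explanatory variables for response. Keep whole-course maximum dose, total duration and later drugs as descriptive.

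These are data definitions and imply no change in clinical management. The cost is an abstraction rule, a stated assessment time and a sentence in the analysis section. The rule should be set before chart review (months 7-12 in Timelines), since a later change means abstracting the charts again. Some early-phase doses will be missing from old charts. Confounding by baseline severity remains and needs separate handling.
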